4.1 First stage (discovery phase)

The first stage (discovery phase) will include at least 30 patients from each of the following groups: MM, pre-MM conditions (SMM and MGUS), HL, aggressive NHL (DLBCL), FL, MZL, AML, MDS and control subjects with no malignant disease.

4.2 Second stage

In the second stage, at least 250 patients with MM and 250 patients with NHL and at least 100 patients with each of the remaining hematological malignancies mentioned above will be tested.

Out of these patients, AML, lymphoma and MM patients will be followed-up at the clinical sites. Periodic sampling will be defined according to disease type and progression rate. Blood and plasma samples will be stored in the clinical sites until relapse diagnosis. At this stage, blood samples will be analyzed retrospectively on the HemaChip. The screening, enrollment and samples collection can begin in the first stage of the trial, in order to allow a maximum follow-up period for at-risk subjects as part of the study, and to meet the recruitment goals.

4.3 Third stage

The last stage consists of screening of a larger group of subjects at risk to develop MM / lymphoproliferative disorder. This stage will include 400 elderly patients (>65 years old) and 500 first-degree relatives of patients (and in particular siblings). The screening, enrollment and sample collection can begin in the first stage of the trial, in order to meet the recruitment goals.

In all stages, the age and sex-matched subgroups will be considered and matched.

4.4 Clinical follow-up

Subjects that serve as controls, subjects at risk (from the Third stage) and a subset of patients from the First and Second stage are expected to donate blood a single time. Following this donation, their participation will end.

For a subset of patients from the Second stage it is expected, after signing the informed consent forms, that serial samplings will be performed during the disease follow-up according to the standard clinical practice and/or recommended schedule and disease assessment plan (see Table 3).

All follow-up patients will be followed for a period of up to 36 months.

For this clinical trial, demographic and baseline parameters including sex, age, race, height and weight, medical history, smoking history and status, details of initial diagnosis and treatment history concomitant medications as well as adverse events (AEs) of special interest (see section 9.1), (serious) AEs related to study procedure, treatment for the disease, disease response and survival status will be collected (as applicable).

Subjects who complete the main study, may be followed up for their disease status, anti-cancer

treatments, concomitant medications, new primary malignancy and survival, following statistical review of the study results. Serial blood samplings will be performed during the long-term follow-up according to the standard clinical practice and/or recommended schedule and disease assessment plan (see Table 3).

A detailed plan for long-term follow-up beyond the main study will be provided as an amendment to this protocol.

4.4.1 Recommended follow-up schedule

Follow-up patients will donate blood periodically according to the following recommendations described in Table 3.

5 STUDY POPULATION

5.1 Number of subjects

First stage: at least 300 subjects.

Second stage: at least 1000 subjects.

Third stage: up to -900 subjects.

The sample size calculations and consideration are presented in section 10.4 below.

The number of participants in the study is described in Table 1 below.

Table 1. Number of participants

	1st Stage	2nd Stage*	3rd Stage*
	No. of Patients/Subjects (at least)	No. of Patients/Subjects (at least)	No. of Patients/Subjects (up to)
MM	30	250	-
MGUS	30	100	-
SMM	30	100	-
HL	30	100	-
DLBCL	30	250	-
FL	30		-
MZL	30		-
AML	30	100	-
MDS	30	100	-
Control (with no malignant disease)	30		
Subjects at risk	-	-	400 Elderly >65 500 First degree relatives

* The screening, enrollment and sample collection can begin in the first stage of the trial, in order to allow a maximum follow-up period for at-risk subjects as part of the study and to meet the recruitment goals.

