3 ENDPOINTS

Primary endpoints:

1. Define a set of biomarkers for each condition. Determine efficiency, sensitivity, specificity, limit of detection.
2. Determine assay efficiency, sensitivity, specificity, limit of detection for each stage.

Secondary endpoints:

1. Determine prognostic value of discovered epigenetic markers.
2. Determine metrics for response to therapy.

Exploratory endpoints:

1. Identify therapeutic targets base on differential epigenetic loci.
2. Determine an MRD protocol for epigenetic follow-up.

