10.3 Interim analysis

A single formal interim comparative analysis of the epigenetic patterns in blood-derived DNA from control subjects with no malignant disease and subjects at risk for developing the investigated hematological malignancies and the patterns obtained for all malignant and premalignant hematological conditions will be conducted after approximately 24 months from the beginning of the study and will include:

Comparative analysis for 250 newly diagnosed NHL samples with HemaChip

Comparative analysis for 250 newly diagnosed MM samples with HemaChip

Comparative analysis for 100 samples of the following conditions: SMM, MGUS, HL, AML, MDS, control subjects with no malignant disease and subjects at risk for developing the investigated hematological malignancies.

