As evident from Figure 1, the larger the deviation of the observed sensitivity from the 80% value, the smaller the sampling size required to prove that the actual sensitivity of the tested discovery array is statistically significantly higher than 80%. In case of the optimistic estimate, it is expected the sensitivity of the chip designed for the disease detection to be 95%, which corresponds to a minimum sample size of 30 subjects for each disease subtype. In the context of the mentioned numbers, and the confidence level of 95%, the confidence interval will be 0.817, and 0.999. In case of the minimum acceptable estimate, the sensitivity of the discovery array is set to be 89%, which corresponds to a sample size range of about 99 subjects per disease. In the context of the mentioned numbers, and the confidence level 95%, the confidence interval will be 0.810, and 0.943.

Since the real sensitivity of the discovery is unknown and based on experience with 60,000 pixel arrays, we have decided to start with a set of 30 subjects and use the data for more precise and evidence based power calculation. The selection of the biomarker panel may be performed even under this uncertainty by including also more variable markers in the HemaChip panel and further tune the array once sufficient data has been accumulated.

Validation stage:

The large discovery chip serves as a matrix for selecting significant markers and as an experimental platform for the final targeted HemaChip design with a reduced number of spots/markers. Here, the same statistics need to be performed to prove that the HemaChip will work with a high statistical accuracy. Since there has been a reduction in markers, we will assume that the sensitivity of the chip will be at a lower level, yet still above the minimum threshold of 80%. With the same test setup (arcsine transformation, significance level = 0.05, test power = 0.8) and the expected specificity of 85% (lower bound), approximately 356 subjects (Sample size) will be needed to verify the results. In the context of the mentioned numbers, and the confidence level 95%, the confidence interval will be 0.810, 0.887 (Figure 12).

The research program is designed to test diagnosed ~250 subjects of MM and NHL, and 100 subjects of the remaining conditions in the validation stage. If the selection of biomarkers was sufficiently good, the expected sensitivity of the HemaChip will not dramatically decline relative to

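### Specificity is a primary endpoint at every stage, but the Stage 2 recruitment numbers contain no non-malignant controls, the interim analysis counts on 100, and Section 10.4 sizes nothing for specificity

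*Protocol*

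**What the plan says.** **Endpoint.** The second primary endpoint in Protocol Section 3 reads: "Determine assay efficiency, sensitivity, specificity, limit of detection for each stage". Primary objective 2 (Section 2) is to validate the platform as a diagnostic tool. Section 10.1 calls comparison with non-malignant controls essential.

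**Recruitment.** Section 5.1 gives "First stage: at least 300 subjects" and "Second stage: at least 1000 subjects". In Table 1 the row "Control (with no malignant disease" shows 30 in Stage 1 and nothing in Stages 2 and 3. Section 4.2 describes Stage 2 as "at least 250 patients with MM and 250 patients with NHL and at least 100 patients with each of the remaining hematological malignancies" named earlier, with no control group. The validation paragraph of Section 10.4 likewise speaks of diagnosed subjects.

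**Interim analysis.** Section 10.3, like the synopsis, plans 250 NHL samples, 250 MM samples and "Comparative analysis for 100 samples of the following conditions: SMM, MGUS, HL, AML, MDS, control subjects with no malignant disease and subjects at risk".

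**Sample size.** Section 10.4 sizes the validation stage on "the expected specificity of 85% (lower bound"), which it says needs about 356 subjects. The only table of sample sizes in that section is headed by expected sensitivity.

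**Matching.** Section 4.3 says age- and sex-matched subgroups will be used in all stages, and Section 10.2.1 promises age-matched controls.

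**The concern.** A diagnostic validation needs people without the target conditions if it is to say how often the test is falsely positive in them. The protocol asks for that quantity in Stage 2 as a primary endpoint, but its enrolment plan and its interim analysis plan disagree on whether such people will be there. Sites recruiting to Table 1 would meet their Stage 2 target with no control enrolled. The contradiction would then surface at about month 24, when the interim analysis looks for 100 control samples.

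A statistical analysis plan can define denominators, but it cannot supply subjects whom the protocol does not enrol. Section 10.4 gives no help on how many controls would be enough, because the one figure it attaches to specificity appears to be a sensitivity calculation.

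**Working it through.** **1. Is there room for controls in the stated totals?** (inputs: Table 1 and Section 5.1)
- Stage 1: 10 rows × 30 = 300, the stated minimum. The 30 controls are one of the ten rows, so controls are counted when they are planned.
- Stage 2: MM 250 + MGUS 100 + SMM 100 + HL 100 + DLBCL/FL/MZL 250 + AML 100 + MDS 100 = 1,000, the stated minimum. Controls left over: 1,000 − 1,000 = 0.

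**2. How does that compare with Section 10.3?**

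| Group | Table 1 | Interim analysis |
|---|---|---|
| MM | 250 (Stage 2) | 250 |
| NHL | 250 (Stage 2) | 250 |
| SMM, MGUS, HL, AML, MDS | 100 each (Stage 2) | 100 |
| Subjects at risk | up to 900 (Stage 3) | 100 |
| Controls | 30 (Stage 1) | 100 |

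The figure of 100 is read as 100 per condition; a pooled 100 would contradict Table 1 for the five diseases. Every group in the interim list has a source in Table 1 except the controls. Even if all 30 discovery controls were counted, 100 − 30 = 70 would have no planned source.

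**3. What does the figure of 356 size?** (inputs: Section 10.4; null 0.80, alternative 0.85, alpha 0.05, power 0.80, arcsine transformation)

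n = [(z_alpha + z_beta) / (2·asin√p1 − 2·asin√p0)]²
- Denominator: 2·asin√0.85 − 2·asin√0.80 = 2.3462 − 2.2143 = 0.1319
- One-sided alpha: (1.6449 + 0.8416) / 0.1319 = 18.85, and 18.85² ≈ 355.4, rounded up to **356**. This matches the plan.
- Two-sided alpha gives 452 and a two-sample version 711; neither matches.

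The same one-sided formula reproduces 13 of the 14 rows of the Section 10.4 table exactly; for 0.95 it gives 28 against the stated 30. Three things show that 356 refers to sensitivity:
- The pair 0.85 and 356 is a row in the column of expected sensitivities.
- The preceding sentence assumes a sensitivity above 80%.
- The Stage 3 paragraph refers back to the Stage 2 figure as the expected sensitivity, and its screening size of 7,120 equals 356 / 0.05. Dividing by a 5% incidence converts required diseased cases into people screened, so 356 counts cases.

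If the 85% against 80% test were really meant for specificity, it would need 356 controls. With 100, the power is Φ(0.1319 × √100 − 1.6449) = Φ(−0.326), about 37% one-sided.

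**4. What precision would controls give?** (exact Clopper-Pearson 95% limits; with no false positives the lower limit is 0.025^(1/n))

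| Controls | Negative | 95% interval |
|---|---|---|
| 0 | – | not estimable |
| 30 | 30 | 88.4% to 100% |
| 100 | 95 | 88.7% to 98.4% |
| 100 | 100 | 96.4% to 100% |

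**The case against.** The strongest reply is that controls are plainly intended. Section 10.3 counts on them, Sections 4.3 and 10.2.1 promise matching, the Stage 2 total is a minimum, and Section 5.5 lets the consortium add samples. Non-applicable cells in Table 1 carry a dash, while the Stage 2 and Stage 3 control cells are blank, so a merged or lost cell is possible. This stands as far as it goes: it would be too strong to say that the sponsor means to validate without controls. But the exact sum to 1,000 and the patient-only text of Sections 4.2 and 10.4 point to none being counted, whatever the blank cell held.

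Three stronger readings are tempting, and the documents support none of them.
- **That Stage 2 would have no negatives at all.** Specificity of one condition against the others remains estimable with hundreds of subjects, and objective 1 asks for that kind of discrimination. Stage 3 evaluates specificity separately, in up to 900 at-risk subjects (900 × 0.95 = 855 unaffected at the protocol's 5%). The gap is specificity against non-malignant subjects in Stage 2.
- **That the 30 discovery controls would be reused, biasing specificity upward.** Nothing says so. They give blood once (Section 4.4), and discovery testing runs on a commercial array (Section 8), so they would have no HemaChip result unless stored material were re-run.
- **That the plan misses a 99.5% benchmark.** That figure appears in Section 1 as background on other studies; the protocol sets no specificity target.

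The wrong word in Section 10.4 changes no number. It matters here only because it hides that specificity is not sized.

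**Conclusion.** The inconsistency is real and wrong as written: the Stage 2 plan in Table 1 and Sections 4.2 and 5.1 counts 0 non-malignant controls, while Section 10.3 counts on 100. Followed to the Table 1 numbers, Stage 2 could not deliver its primary specificity endpoint against people without malignancy, although between-disease specificity would survive. No sample size in Section 10.4 supports specificity; the 356 is a sensitivity figure under the wrong name.

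This rests on reading the stages in Section 3 as study stages and the interim figure of 100 as per condition. The mislabelling is an inference, but the table heading, the surrounding text and 356 / 0.05 = 7,120 all agree on it.

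**What to change.** - Enter the 100 controls that Section 10.3 already assumes into Stage 2 in Table 1, Sections 4.2 and 5.1 and the synopsis: 1,000 + 100 = a minimum of 1,100.
- State that they are new subjects, separate from the 30 discovery controls, tested on the HemaChip, and matched on age and sex as Sections 4.3 and 10.2.1 already promise.
- Name them as the denominator for Stage 2 specificity against non-malignant subjects, and report between-disease specificity separately.
- In Section 10.4, change the 85% specificity to 85% sensitivity, and add the expected precision for specificity at n = 100 (for example 95/100, exact 95% interval 88.7% to 98.4%).
- If no Stage 2 controls will be enrolled, correct Section 10.3 and the synopsis, and limit the Stage 2 specificity claim to between-disease discrimination. Stage 3 subjects are not a good substitute: their work-up (SPEP, FLC, chemistry, blood count) is directed at myeloma and is a weak reference for lymphoma, AML or MDS.

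Cost: a protocol amendment that formally adds up to 100 single-draw controls to the enrolment table. The alternative needs no new subjects but gives up part of the Stage 2 claim.

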5.2 Eligibility

5.2.1 Inclusion criteria

Subjects must meet all of the following inclusion criteria to be enrolled in the trial:

General criteria for all study populations:

1. Male and female subjects ≥ 18 years of age;
2. Ability to understand and willingness to sign a written informed consent document.

For patients with hematological malignancies:

1. Patients who have been diagnosed, have measurable disease and / or are being monitored / followed-up due to one of the following conditions: MM, pre-MM conditions (SMM and MGUS), HL, aggressive NHL (DLBCL), FL, MZL, AML, MDS that did not yet undergo any treatment.

NOTE: Patients diagnosed with DLBCL that is transformed from FL or MZL, and patients diagnosed with AML secondary to MDS or MPN, that were treated for their primary disease (FL/MZL/MDS/MPN) prior to study enrollment, are eligible. .

For subjects at risk for developing the investigated hematological malignancies:

1. First degree relatives;
2. Elderly subjects ≥ 65 years of age.

5.2.2 Exclusion criteria

Subjects meeting any of the following exclusion criteria will not be enrolled in the trial:

1. Patients/subjects with current co-diagnosis of another type of cancer;
2. Patients/subjects with a known active or prior cancer (other than defined as study population), occurring within the last 2 years (even if considered to be in complete remission). Patients/subjects with nonmelanoma skin cancer or carcinoma in situ of any type are not excluded if they have undergone complete resection;
3. Patients/subjects with active inflammatory autoimmune disease that requires treatment with immunosuppressive/ immunomodulation agents;

4. Patients/subjects with known human immunodeficiency virus (HIV) positive;
5. Patients/subjects with known active Hepatitis A/B/C or past Hepatitis C
6. Subjects that are likely to be noncompliant with the protocol, or felt to be unsuitable by the investigator for any other reason.

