2 STUDY OBJECTIVES

The primary and the secondary objectives of this clinical trial are defined as follows:

Primary objectives:

1. Biomarker discovery - define a set of differential epigenetic biomarkers that uniquely identify the following conditions: MM, pre-MM conditions [smoldering MM (SMM) and monoclonal gammopathy of undetermined significance (MGUS)], HL, aggressive NHL [diffuse large B cell lymphoma (DLBCL), FL, MZL, AML, MDS and control subjects with no malignant disease .
2. Validation – validating the discovery platform (HemaChip) as a diagnostic tool for various hematological malignancies.
3. Towards early detection - Patients, at risk of relapse tested periodically to evaluate early detection capability of the HemaChip.
4. Towards population screening - evaluate the sensitivity and specificity for screening in populations at risk for developing the investigated cancers: (i) elderly (>65 years old) at high risk to develop MM; (ii) first degree relatives of the conditions described above.

Secondary objectives:

1. Evaluate the correlation between epigenetic status and well-known prognostic markers, including known genetic markers.
2. Predict response to therapy.

Exploratory objectives:

1. Identify new therapeutic targets based on epigenetically modified genomic loci.
2. Provide prognostic information at pre-treatment and monitoring of MRD.

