10 STATISTICAL CONSIDERATIONS

10.1 Study design

Controlled study - This study aims to identify methylation patterns indicating the presence of cancer. Comparison to control participants with no malignant diseases is essential for identifying tumor-specific methylation patterns.

Open study - The current study is an open study where all participants are divided into known groups. For the first stage of the study, the group identification is essential for discovery of biomarkers for each disease type. Discovery stage will be based on empirical comparison between controls and patients diagnosed with various hematological cancers. Therefore, group identification is required for validation, comparison with state-of-the-art diagnosis and disease status.

The current study contains only one type of intervention and therefore randomized/crossover or parallel groups are inapplicable.

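### The eligibility wording admits people with a known or past target condition to the Stage 3 screening cohort and does not clearly keep known MGUS, SMM or MDS out of the controls

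*Protocol*

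**What the plan says.** Exclusion criterion 2 in section 5.2.2 applies to patients and subjects alike and removes those with a "known active or prior cancer (other than defined as study population), occurring within the last 2 years". Criterion 1 removes "Patients/subjects with current co-diagnosis of another type of cancer".

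Section 5.2.1 has three inclusion blocks. The first, "General criteria for all study populations", asks for adult age and consent. The second, for patients, lists the target diseases and carries the requirement of no prior treatment, with a note on transformed and secondary disease. The third is headed "For subjects at risk for developing the investigated hematological malignancies" and has two entries: first-degree relatives, and "Elderly subjects ≥ 65 years of age". There is no block for controls. They appear in Table 1 (section 5.1) as "Control (with no malignant disease", and section 10.1 says: "Comparison to control participants with no malignant diseases is essential for identifying tumor-specific methylation patterns".

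The fourth primary objective (section 2) is to "evaluate the sensitivity and specificity for screening in populations at risk for developing the investigated cancers". Stage 3 plans 400 elderly subjects and 500 relatives.

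**The concern.** The exemption in criterion 2 stops patients from being excluded by their own index disease. Because it is not tied to the patient cohorts, it also applies to the two groups that are meant to be free of known target disease.

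In Stage 3 the aim is to learn how the HemaChip performs in people whose disease status is not yet known. A person who already carries a diagnosis is not a screen-detected case. Including such people mixes diagnostic performance into an estimate of screening performance, and this is a primary objective.

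Among controls, a known carrier of MGUS, SMM or MDS has a condition that is also one of the target classes. The discovery comparison may rest on as few as 30 controls, so each misplaced person is 1/30, or 3.3%, of the reference group.

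**Working it through.** **Which listed criteria stop a person with a known target condition?**

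| Criterion | Stage 3 at-risk subject | Control |
|---|---|---|
| General inclusion (5.2.1) | No | No |
| Cohort inclusion (5.2.1) | No: kinship or age is enough | No block exists |
| No prior treatment (5.2.1) | No: patient block only | No: patient block only |
| Exclusion 1 | Not clearly: for someone in no disease cohort, the other cancer has nothing to be compared with | Same |
| Exclusion 2 | No: target cancers are exempt, and MGUS and SMM are not plainly cancers | Same |
| Exclusion 6 | Only at the investigator's discretion | Same |
| Heading or label | Points against a diagnosed malignancy, but a known MGUS or SMM carrier is at risk of developing MM | Bars active malignancy; unclear for MGUS, SMM, MDS and remission |

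**Does the control label cover premalignant conditions?** The protocol's own vocabulary suggests not. Section 1 describes MPN/MDS as pre-malignant, section 10.3 separates malignant from premalignant conditions, and section 5.2.1 calls SMM and MGUS pre-MM conditions. Yet the patient block in 5.2.1 places all of these under a heading about haematological malignancies, so usage is inconsistent.

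**Is there a laboratory check?** Table 2 and section 7.1 give Stage 3 subjects an MM laboratory profile at screening, but no eligibility consequence is attached. Controls do not have it.

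**The plan's own Stage 3 figures (section 10.4).** The validation-stage requirement of 356 diseased subjects and a frequency of about 5% in the risk cohort give 356 / 0.05 = 7120, as stated. With the planned 400 + 500 = 900 subjects, 900 × 0.05 = 45 cases. No figure in the protocol is wrong on this point.

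**Illustrative effect on Stage 3 sensitivity.** Take 45 undiagnosed cases with true sensitivity s, and add k known cases detected at 0.95. The values of s, k and 0.95 are assumptions, and the k cases are taken as additional to the 45.

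Apparent sensitivity = (45·s + 0.95·k) / (45 + k)

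For s = 0.60 and k = 10: (27 + 9.5) / 55 = 0.664.

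| True sensitivity | k = 5 | k = 10 | k = 20 |
|---|---|---|---|
| 0.40 | 0.455 | 0.500 | 0.569 |
| 0.60 | 0.635 | 0.664 | 0.708 |
| 0.80 | 0.815 | 0.827 | 0.846 |

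**Opposite direction.** If the ten were treated people in remission, all counted as diseased and none testing positive, the result would be 27 / 55 = 0.49. If they were counted as disease-free, sensitivity would not change and they would enter the specificity estimate instead.

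**The case against.** The case against rests on the cohort definitions. The protocol repeatedly defines controls as having no malignant disease and calls that comparison essential. Table 1 lists diagnosed conditions and at-risk subjects on separate rows, and section 10.1 says participants fall into known groups. A person already diagnosed with MM is no longer at risk of developing it. The purpose of the exemption is evident, medical history is recorded at screening, and an investigator may decline an unsuitable subject.

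Much of this stands, and it limits the point in four ways.

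- A reader might infer that someone with active MM, lymphoma or AML can enter as a control. The label rules that out.
- A reader might blame the exemption for MGUS and SMM carriers among controls. Criterion 2 concerns cancer. If these conditions are premalignant, it would not catch them even without the exemption. That gap comes from the missing control criteria.
- A reader might infer that known cases must inflate sensitivity. The at-risk block has no untreated requirement, so people in remission could enter and test negative.
- A reader might size the control problem from the population prevalence of MGUS. The protocol gives no prevalence, and any such rate includes undiagnosed carriers whom a history-based rule would not remove. The relevant rate, known carriers offered as controls, cannot be obtained from the protocol.

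What does not stand is reliance on the at-risk heading and on discretion. The heading fits a known MGUS or SMM carrier exactly, and objective 4 describes the elderly group as at high risk of MM. Across four sites, discretion is no substitute for a stated criterion.

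**Conclusion.** The point holds as a defect in eligibility wording. The exemption in criterion 2 has the wrong scope, the at-risk criteria do not exclude a known or past target condition, and controls have no criteria to settle MGUS, SMM, MDS or a malignancy in remission.

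The size is uncertain. With 5 to 20 known cases detected at 0.95, added to 45 undiagnosed cases, apparent sensitivity rises by 1.5 points (true 0.80, five added) to about 17 points (true 0.40, twenty added). The central illustration is 0.60 to about 0.66. The 45 rests on the plan's 5%; every other input is assumed. The direction may reverse if the known cases are in remission, so the supported statement is that Stage 3 accuracy can be biased, not that it will be inflated. No magnitude is claimed for controls, and no sample size in the protocol changes. A correction is worthwhile because a primary objective is affected and the remedy is small.

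**What to change.** Amend section 5.2 and the matching synopsis entries:

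1. Limit the exemption in exclusion criterion 2 to the patient cohorts.
2. Add a criterion for controls and at-risk subjects: no known current or previous haematological malignancy, and no known MGUS, SMM or MDS, checked from the medical history already recorded at screening.

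The second change is needed as well as the first. Narrowing the exemption alone would leave premalignant conditions and target cancers older than the two-year window uncovered.

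For people already enrolled, use the recorded history to flag those who do not meet the new criterion, and leave them out of the control and Stage 3 accuracy analyses.

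The cost is a short amendment, a review of existing records, and a few subjects excluded or reclassified. No new test is required. The rule does not remove undiagnosed carriers. In Stage 3 they are among the people screening is meant to find; among controls they remain a limitation.
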